- (2) have a current diagnosis of PTSD (As determined by the Clinical Administered PTSD Scale to diagnose PTSD resulting from trauma that occurred in the past 30 days; this structured interview measures the symptoms of PTSD corresponding to DSM–IV criteria)

Women who meet the threshold criteria will be invited to participate in the first step of the study: participation in the Asian Women Discussion group, which consists of 10 psychotherapy sessions and an additional post-intervention meeting. This focus group will provide crucial feedback to help refine the sessions. Because only ten women who meet the eligibility guidelines will be selected: most women will not be selected.

F.3. Exclusion criteria (Indicate if you have different exclusion criteria for different cohorts)

Exclusion criteria. Women who meet any of the following criteria will be ineligible for the study:

- (1) Significant current risk of homicidal or suicidal behavior (deliberate self-injury where there is at least some admitted or inferred intention to die; particularly, participants who have had a suicide attempt within the past year or participants with active suicidal ideation with intent or plan)
- (2) Presence of schizophrenia, schizoaffective, or organic mental disorders using DSM-IV criteria
- (3) Women of mixed race (i.e., those who do not identify as 100% Chinese, Korean, or Vietnamese or a mixture thereof)
- (4) Victims who have experienced natural disasters or other non-violent trauma only (i.e., those who have not been traumatized by physical or sexual violence)
- (5) Women who are currently victims of severe Intimate Partner Violence (IPV) using The Revised Conflict Tactics Scale (CTS2).
- (6) Women who experience worse outcomes than baseline two weeks after the study begins will be withdrawn from the study.

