Justification for Exclusion Criteria: We aim to create a homogeneous sample with regard to heterosexual female victims of violent trauma. The reason for excluding victims of non-violent trauma is because studies have found that assaultive violence is more likely to lead to PTSD and that victims of assault exhibit more elevated PTSD symptoms compared to victims of non-violent trauma or natural disasters. We specifically include 1.5 and 2nd generation children of immigrants due to the elevated health risks and various stressors that are acculturation-related. We expect that approximately 10 % of the subjects experience current IPV based on the epidemiological data on IPV among API women indicating 1.6 % of API women reported severe IPV vs. 9.2 % experiencing less severe types of IPV. We have decided to exclude severe types of IPV because of our concern that participation in intervention among those who reported severe current IPV may increase risk of IPV although Melendez et al. has shown that there was no increase in IPV among those who completed 8 weekly sessions of Project FIO.

F.4. Study procedures

In the box below provide a detailed description of the study including **all the procedures to be performed** (preferably in sequential order). Be sure to specify which procedures are experimental (i.e. testing a new intervention for psychiatric illness) versus which procedures are standard of care. Be sure to include the following information:

- Methods of data collection
- Details regarding experimental interventions
- Number, frequency and duration and types of subject contacts (visits, phone calls, internet surveys, mailings, etc.)
- Duration of participation for single subject
- Anticipated duration of the entire study (up to and including data analysis)
- ***Note, for complex studies it may be useful to attach visit calendars and charts that indicate which interventions will occur for which group at which time

Study Procedures

Overview: Our intervention research study, “Asian Women’s Action for Resilience and Empowerment (AWARE): A Stage IA and IB Intervention Development Study, will be comprised on 3 groups of participants:

1) *Asian Women Discussion Group*

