6. In Year 2, we will recommence our recruitment efforts to identify and enroll eligible women into the intervention group and the wait-list group. The interviews during the screening process will be audio-recorded. Women who will be screened in Year 2 go through the same process as women who screened in Year 1 for Asian Women Discussion Group and must meet the same eligibility requirements (see Step 2 and Step 3).
7. Our goal is to screen about 400 women in Year 2. Of this number, we expect about 30% (n=120) to meet all eligibility criteria. We will randomly select 96 eligible women and assign 48 to the AWARE intervention group and 48 to the wait-list group.
8. Individual participation in the AWARE intervention group includes:
 - a. Written consent to participate including consent for the audiotaping of each session.
 - b. Completion of a baseline assessment prior to the start of the group sessions.
 - c. Participation in 105-minute group sessions each week (for a total of 8 weeks) with a small group of other participants and a clinician, covering topics including: Safety, Taking Good Care of Yourself, Compassion, Commitment, Creating Meaning, Setting Boundaries in Relationships, Coping with Triggers, Healthy Relationships, Self-Nurturing, and The Life Choices Game
 - d. \$26 payment and \$4 transportation reimbursement for each weekly group session and \$20 payment and \$4 transportation reimbursement for each assessment.
 - e. Completion of a weekly Adverse Events Log and a weekly questionnaire on the AWARE stories.
 - f. Receipt of and response to daily, secure mobile text messages (called “AWARE Stories”) in between each weekly session to reinforce participation and adherence
 - g. Completion of assessments upon the last intervention session
 - h. Completion of outcome assessments in a follow-up visit 3 months after the last intervention session
9. Individual participation in the wait-list group includes:
 - a. Written consent to participate including consent for the audiotaping of each session.
 - b. Completion of a baseline assessment prior to the start of the group sessions.
 - c. Participation in 90-minute group sessions each week (for a total of 8 weeks plus an additional post-intervention meeting) with a small group of other participants and a clinician, covering topics including: Safety, Taking Good Care of Yourself, Compassion, Commitment, Creating Meaning, Setting Boundaries in Relationships,

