Quantitative data for protocol evaluation and participant psychometric monitoring: We will evaluate participants in the Asian Women Discussion Group by comparing the results of pre-intervention and post-intervention psychometric measures. These comparisons will be used to determine if the current protocol is achieving the intervention's goals of providing benefits to participant's mental and behavioral health.

Data Analysis for Aim 2 (year 2):

(1) Feasibility Analysis of group psychotherapy: We conservatively anticipate that 15% of participants will dropout during the 8 week RCT. We also anticipate that another 5% will dropout at the 3-month follow-up evaluation. The first stage of analysis will involve estimating the proportion of women who are eligible and agree to enroll in the study. A 95% confidence interval for the proportion will also be produced. Then, among those who enroll, baseline characteristics will be compared between those randomized to the intervention and those randomized to the wait-list control group to assess balance.

We will estimate the proportion of women who adhere at 8 weeks and 3-month follow-up. Mean proportion of women who attend (at 8 weeks and 3-month follow-up) and 95% confidence intervals will be generated for the total sample and then by groups. We will test the

difference between the participants' adherence rates in the intervention and control group at 8 weeks and 3-month follow-up using a chi-square test. We will then examine bivariate associations between baseline characteristics and attrition (each time point considered separately) using chi-square tests for categorical variables and two sample t tests for continuous variables among all participants. Multivariable associations will be examined using multiple logistic regression models for adherence by group, relating those characteristics that were significant in bivariate analysis to attrition, if sample size permits.

(2) Feasibility Analysis of AWARE Stories (Hypothesis for secure mobile messaging): Higher level of satisfaction and higher utilization of secure text messages are positively associated with group psychotherapy attendance. Ordinal chi-square tests will be used to examine the association between ordinal scale (1-4) of messaging satisfaction and utilization questions and psychotherapy attendance.]

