(3) Safety analysis (Hypotheses for safety): For the safety measure, participants will be asked to keep a Weekly Adverse Event Log for measuring safety outcomes (including IPV, suicidal ideation, suicide attempts, and self-mutilation). Our hypotheses are: (A) The AWARE group will have statistically significant lower proportions of suicidal ideation, suicide attempt, and self-mutilation at 8 weeks and 3-month follow-up, compared to baseline. (B) There will be no increased frequency of IPV among the AWARE group between the baseline and post intervention. McNemar's tests will be used to test both (A) and (B). Safety outcomes are measured as developments of adverse event outcomes over the course of the study. These include: (1) suicidal ideation, (2) suicide attempts, (3) self-mutilation, (4) and frequency of IPV. We will estimate the proportion of each adverse event at 95% confidence intervals for participants in the intervention group. We will employ McNemar's tests to compare the proportions of each adverse event in the AWARE group at baseline to the ones in the wait-list group. In addition, mixed effects models for adverse event outcomes will be performed, adjusting for baseline characteristics, such as psychiatric diagnosis severity and substances use, to measure the impact of the baseline characteristics on adverse events and also the pattern of change in adverse events from baseline to the post-intervention follow-up.

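### The one between-arm safety test that the protocol spells out sets AWARE's pre-treatment proportion against an undated wait-list proportion, and uses a paired test on two unmatched arms

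*Protocol*

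**What the plan says.** All of this is in the protocol.

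- **Section G.3, Aim 2, (3) Safety analysis.** Two hypotheses are set within the AWARE arm: (A) lower proportions of suicidal ideation, attempt and self-mutilation at 8 weeks and 3 months than at baseline, and (B) no rise in IPV from baseline. McNemar's test is named for both. A further sentence then uses McNemar's tests to "compare the proportions of each adverse event in the AWARE group at baseline to the ones in the wait-list group". No time point is attached to the wait-list value.
- **Same paragraph, outcome definition.** "Safety outcomes are measured as developments of adverse event outcomes over the course of the study".
- **Same paragraph, models.** Mixed models adjusted for baseline characteristics are to describe "the pattern of change in adverse events from baseline to the post-intervention follow-up". No arm term is mentioned.
- **Section F.4, Detailed Procedure, item 7.** "We will randomly select 96 eligible women and assign 48 to the AWARE intervention group and 48 to the wait-list group". No matching is described anywhere.
- **Section F.4, item 8b.** The baseline assessment comes before the group sessions start.
- **Section F.4, Overview, and items 9g and 9h.** The wait-list receives the same intervention 3 months after AWARE starts. The post-baseline assessments listed for it are at its own last session and 3 months after that.
- **Section G.3, Aim 2, (1) Feasibility.** For a different outcome the plan does use an independent-groups test between arms: "adherence rates in the intervention and control group at 8 weeks and 3-month follow-up using a chi-square test". The same paragraph expects 15% dropout during the 8 weeks.

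**The concern.** There are two faults in one sentence.

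**The contrast.** The AWARE side is fixed before treatment begins, so nothing that happens to AWARE women during or after the sessions can enter it. This conflicts with the same paragraph's definition of safety outcomes as events that develop during the study.

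**The test.** McNemar's test works on discordant pairs. With two independently randomised groups there are no pairs, so the statistic is undefined until someone invents a pairing, and the p-value then depends on that choice.

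At stake is the safety conclusion of a pilot whose Year 2 purpose is feasibility and safety. The within-AWARE tests of (A) and (B) are correctly paired, but they cannot separate an effect of AWARE from change that would have happened anyway. The comparison with the wait-list is what could do so, and as written it does not.

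**Working it through.** The protocol gives no power or expected result for this comparison (section G.2 states that no formal calculation is needed), so there is no figure to reproduce.

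**Step 1: what the sentence compares, by reading of the wait-list value**

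| Wait-list value taken at | What the test is |
|---|---|
| Baseline | A check of baseline balance, which section G.3 already provides elsewhere |
| A later visit, still untreated | AWARE before against wait-list after: arm confounded with time |
| After the wait-list's own course (items 9g, 9h) | AWARE women before treatment against wait-list women after it: AWARE can move the wait-list side, but arm and time are still mixed and there is no untreated concurrent group |

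**Step 2: dependence on the pairing**

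Let k be the number of invented pairs in which both women have the event. With x and y events in the arms, the discordant counts are b = x − k and c = y − k. The exact p-value is 2·P(Bin(b + c, 0.5) ≤ min(b, c)). Two assumed tables:

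- 10/48 against 19/48. With k = 10: b = 0, c = 9, p = 2 × 0.5⁹ = 0.004. With k = 0: b = 10, c = 19, p = 0.136. Fisher's test, which needs no pairing, gives 0.074.
- 5/48 against 13/48. With k = 5: b = 0, c = 8, p = 2 × 0.5⁸ = 0.008. With k = 0: b = 5, c = 13, p = 0.096. Fisher gives 0.065.

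These are the extremes over all possible pairings.

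**Step 3: sensitivity to harm in the AWARE arm**

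Inputs: 48 per arm (F.4, item 7); level 0.05 (G.3), taken as two-sided; 15% dropout by 8 weeks (G.3), so 48 × 0.85 = 40.8, about 41 per arm. Event rates are assumptions. The nearest anchor in the protocol is that "approximately 10 % of the subjects experience current IPV" (F.3, justification), a figure that precedes the exclusion of severe IPV. Rates for attempts and for the most serious ideation should be lower, since F.3 excludes "participants who have had a suicide attempt within the past year or participants with active suicidal ideation with intent or plan".

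Method: exact enumeration of two independent binomial counts. For McNemar, k follows the hypergeometric distribution that random pairing implies; the uncorrected version rejects when (b − c)²/(b + c) > 3.84.

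Scenario: AWARE starts at 10% and rises by 8 weeks, while an untreated wait-list stays at 10%. The written test then compares 10% with 10%, however large the rise.

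| Test | AWARE rises to 20% | AWARE rises to 30% |
|---|---|---|
| As written, 48 per arm (uncorrected / exact McNemar) | 4.4% / 2.0% | 4.4% / 2.0% |
| Same visit, 48 per arm (chi-square / Fisher) | 29% / 18% | 72% / 61% |
| Same visit, 41 per arm (chi-square / Fisher) | 25% / 17% | 65% / 55% |

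**Step 4: the opposite error**

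Suppose the wait-list value is a later untreated visit and both arms fall equally from 10% to 5%. The written test compares 10% with 5% and rejects in 14% (uncorrected) or 6% (exact) of trials although AWARE does nothing. Chi-square and Fisher give 17% and 6% on the same mismatch, so the cause is the unequal time points and not McNemar's test.

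**The case against.** **The mixed models may fill the gap.** The safety models are not restricted to AWARE, and the pilot evaluation that follows in G.3 uses mixed models to compare change between groups. An arm-by-time term is a fair expectation, and its specification could sit in an analysis plan that is not at hand. This stands in part. But the safety paragraph states no arm term, the later paragraph introduces its models for efficacy outcomes, and neither corrects a sentence that is explicit about its contrast and its test.

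**The word baseline may be a slip.** That is possible, but nothing else in the protocol corrects it, and removing it would still leave a paired test on unpaired arms.

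**A reader might infer that no effect of AWARE could ever alter this test.** That is too strong. Items 9g and 9h can place the wait-list's assessments after its own AWARE course, and an effect would then enter from that side. What holds is that the AWARE arm's own response cannot enter.

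**A reader might infer that McNemar's test is wrong throughout the safety section, or that arbitrary pairing inflates false positives.** Neither is supported. The test suits (A) and (B), which compare the same women over time. Under random pairing with equal 10% rates the rejection rate is 4.4% or 2.0%. The fault is that one trial's p-value is not determined by its data.

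**A reader might infer that harm would go unnoticed.** The protocol's weekly review, event logs, C-SSRS and CTS2 assessments and escalation steps do not depend on this p-value. The fault lies in the reported comparison, not in the protection of participants.

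**Conclusion.** The point holds, and it should be fixed. The stated between-arm safety test cannot register harm or benefit in the AWARE arm, gives a treated-versus-untreated contrast on none of its three readings, and applies a paired test where no pairs exist. The fault is confined to that sentence.

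The structural part rests on the text alone. The size rests on assumed event rates and on an untreated wait-list: about 4% or 2% rejection as written, against 65% (chi-square) or 55% (Fisher) for a same-visit comparison of 30% with 10% at 41 per arm. For a rise to 20%, even the right comparison has only 25% or 17% power, so the pilot can exclude only large differences. The 41-per-arm figures also treat dropout as unrelated to the events. Section F.3 (item 6) and section H.1 withdraw women who worsen or show certain symptoms, so that may not hold unless their events are counted.

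**What to change.** Replace the sentence with, for example:

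*The proportion of women with each safety outcome at the 8-week visit, while the wait-list is untreated, will be compared between AWARE and wait-list by randomised arm, as a risk difference with 95% CI and Fisher's exact test. Women withdrawn for worsening or safety reasons are counted using events recorded up to withdrawal, and the number with missing 8-week data is reported by arm.*

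Keep McNemar's test only for before/after comparisons within the same women.

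The 8-week visit is chosen because AWARE's 3-month visit falls 3 months after its last session, about 5 months after its start (8 weeks plus 3 months), while the wait-list begins its course 3 months after AWARE starts. Sections E.5.B (assessments at baseline, 8 weeks and 3 months), F.4 Overview and F.4 items 9g and 9h must be reconciled so that the wait-list's 8-week assessment clearly falls before its delayed course.

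**Cost.** One analysis sentence and one clarification of visit timing, with no new instrument or endpoint. Precision remains limited: the 95% half-width is 1.96·√(2p(1 − p)/41), about 13 percentage points at a 10% rate and 20 at an assumed 30% rate. The confidence interval should therefore carry the reporting, and a non-significant result should not be read as evidence of safety.

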The participants for the intervention program, Asian Women's Action for Resilience and Empowerment (AWARE) will be comprised of 106 women in total: 10 in the Asian Women Discussion focus group, 48 in the intervention group, and 48 in the wait-list group. The 10 women in Asian Women Discussion Group will participate in the focus group prior to the pilot randomized clinical trial (RCT). We will launch the AWARE campaign to reach out to API women in the greater Boston area and enroll eligible women in our study, using a two-armed randomized design: (1) a group that will receive the 10-session AWARE intervention (n=48) and (2) a wait-list control group who will receive no treatment (n =48). In order to successfully recruit the 96 AWARE participants, we estimate screening 500 women in the community.

G. 2. Sample size justification

Indicate why you chose the sample size proposed. Provide your sample size calculations. If this is a pilot study, this justification does not necessarily require a formal sample size calculation, but should provide a rationale for choosing the sample size proposed (e.g. to estimate a mean to a certain accuracy, to determine if the response rate is above a certain percentage, etc.) **Note: Once the IRB approves a certain study sample size then you may not enroll beyond that sample size without first obtaining approval from the IRB. ****** In determining your sample size be sure to allow for screen failures and study drop-outs in your calculations. Explain how many evaluable subjects you will need to end up with to answer your study question and how many subjects you will need to enroll and consent to achieve this number. The IRB counts study subjects a being enrolled once they have consented.

Our study is a pilot study which does not require a formal sample size calculation.

G. 3. Data Analysis

Provide a description of your plan for data analysis.

- State the types of comparisons you plan (e.g. comparison of means, comparison of proportions, regressions, analysis of variance).
- Which is the PRIMARY comparison/analysis?
- How will the analyses proposed relate to the primary purposes of your study?
- If you are doing qualitative research please state how comparisons will be made.

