Evaluation of Pilot RCT Analysis: We will use an intention-to-treat (ITT) analysis, which indicates all women who are randomized will be included for analysis. To test the success of the randomization, prognostic factors including baseline education, psychiatric diagnosis severity, and substance use will be compared between participants in the intervention group and wait-list group using chi-square tests. Baseline characteristics that show imbalance between groups will be adjusted in multivariate regression models. The efficacy outcome variables will be analyzed as either dichotomized or continuous variables. For PTSD, continuous measures of the CAPS will be assessed. In order to sensitively capture any changes in PTSD scores, continuous measure will be chosen. For HIV outcomes, we will use both dichotomous and continuous variables to measure status and severity of the outcomes at baseline, 8 weeks, and 3-month post-test. Mixed effects models will be used to compare the pattern of change in dichotomous and continuous outcomes over time between groups using normal and logit links, respectively. We will first use an unstructured covariance matrix to

account for correlation between repeated measurements in the same participant and compare it to other covariance structures, using goodness of fit. The most suitable covariance matrix will be chosen for the final model. The same approach will be followed for secondary outcomes. All statistical testing will be performed at the significance level of 0.05 using SAS 9.3.102. Additionally, in order to explore whether compliance affects outcome measures, we will compare the sexual risk behavior, psychiatric severity, and substance use measures between those who drop out versus those who complete the intervention using two-tailed, independent samples t-tests.

Data analysis for Aim 3 (year 2 and 3):

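### The efficacy models take their covariates from a baseline imbalance check, so the adjustment set is fixed only after the arms have been compared

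*Protocol*

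**What the plan says.** The rule is in the protocol, section G.3 Data Analysis, under Evaluation of Pilot RCT Analysis. It appears once for Aim 2 and again in identical words for Aim 3.

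- Purpose and factors: "To test the success of the randomization, prognostic factors including baseline education, psychiatric diagnosis severity, and substance use will be compared", with the comparison made "between participants in the intervention group and wait-list group using chi-square tests".
- Consequence: "Baseline characteristics that show imbalance between groups will be adjusted in multivariate regression models".
- Level: "All statistical testing will be performed at the significance level of 0.05". No separate threshold for imbalance is given.
- Efficacy model: mixed effects models on baseline, week 8 and 3-month data, comparing the pattern of change between groups and starting from an unstructured covariance matrix. No covariate is named in advance, and secondary outcomes are to be handled in the same way.

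The adverse-event mixed models in the safety analysis (G.3, Aim 2, item 3) adjust for baseline characteristics such as psychiatric severity and substance use, with no imbalance condition attached.

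**The concern.** Whether a covariate belongs in a randomised comparison depends on how well it predicts the outcome, not on whether the arms happen to differ on it. If allocation was random, a significant baseline difference is a chance event, so the test can neither confirm nor refute the success of randomisation. Used as a gate for adjustment, it has three effects:

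- The covariate set is unknown until the arms have been compared.
- A prognostic factor is nearly always left out, because a chance imbalance seldom reaches significance at this sample size.
- An imbalance just short of significance stays in the treatment estimate.

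Chi-square is also the only test named for this comparison, so a severity measure that is continuous would have to be cut into categories to be tested. Elsewhere in G.3, the attrition analysis uses t tests for continuous baseline variables.

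The pilot is meant to inform a larger trial (Section D; I.2), so its estimates should come from a model that another analyst could have written down beforehand.

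**Working it through.** The plan gives no figure to reproduce: "Our study is a pilot study which does not require a formal sample size calculation" (G.2).

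**Inputs from the protocol.** 48 per arm (F.4, step 7: "We will randomly select 96 eligible women and assign 48 to the AWARE intervention group and 48 to the wait-list group"); level 0.05; three named factors, in an open list. **Reading adopted:** show imbalance means p<0.05 on the comparison described.

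**1. How often a factor is left out.** Under randomisation each test is significant with probability 0.05, so a given factor is omitted in about 1 − 0.05 = 95% of trials. Three independent tests flag at least one factor with probability 1 − 0.95³ = 14.3%. The list is open, so this is illustrative; ten factors would give 1 − 0.95¹⁰ = 40.1%.

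**2. Largest imbalance that passes as balanced.**

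- Continuous factor: the standard error of the standardised difference is √(2/48) = 0.204, so the threshold is 1.96 × 0.204 = 0.40 SD. At z = 1.9 the difference is 0.39 SD and is not flagged.
- Binary factor, no continuity correction: 24/48 against 33/48 has pooled proportion 57/96 = 0.594. The difference is 0.1875, so z = 0.1875/√(0.594 × 0.406 × 2/48) = 1.87, p = 0.06, not flagged. At 34/48, z = 2.09 and it is flagged. A gap of about 19 points therefore goes unadjusted.
- An observed imbalance above 0.2 SD arises by chance with probability 2 × [1 − Φ(0.2/0.204)] = 33% per factor; only about 5% exceed 0.40 SD.

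**3. Overall type I error.** Simulation of 20,000 trials per setting, assuming one continuous post-baseline outcome, no dropout, one factor split at its median for the test, and factor–outcome correlation of 0.3, 0.5 and 0.7:

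| Analysis | 0.3 | 0.5 | 0.7 |
|---|---|---|---|
| Protocol's rule | 4.9% | 4.4% | 3.9% |
| Covariate prespecified | 5.2% | 4.7% | 4.9% |

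The rule is slightly conservative, not inflating.

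**4. Precision in a model like the one planned.** The planned contrast is change over time by group. A covariate entered as a main effect adds the same amount at every visit and subtracts out of change. In a three-visit fit with unstructured covariance and complete data, the group-by-time estimates and standard errors with and without such a term were identical. The covariate has to act on post-baseline values to matter.

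Take a follow-up outcome adjusted for its own baseline. Assume a baseline-to-follow-up correlation of 0.5 and a factor correlating r with the outcome at both visits. Baseline alone leaves residual variance 1 − 0.25 = 0.75; adding the factor leaves 1 − 0.25/(1 − r²).

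- r = 0.3: 0.725, standard-error ratio √(0.725/0.75) = 0.983.
- r = 0.5: 0.667, standard-error ratio √(0.667/0.75) = 0.943.

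These are reductions of 1.7% and 5.7% in large samples. Simulated at 48 per arm, where the extra coefficient has to be estimated, they become 1.1% and 5.2%. The gain is larger if the factor predicts follow-up beyond the baseline outcome.

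**The case against.** **On size.** A reader might infer a large loss. If a single post-baseline outcome were compared, always adjusting for a factor correlated 0.3 to 0.5 with it would remove 9% to 25% of residual variance (r²). With an assumed 0.5 SD effect, simulated power would be 71% to 80%, against 68% under the protocol's rule. That is not the planned model. The baseline outcome is already a response in the mixed model, and a covariate main effect leaves the continuous change contrast essentially unchanged. This objection stands, and it limits the precision claim to the few per cent shown above.

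**On type I error.** A reader might also infer inflation. Conditional on an imbalance of z = 1.9, the unadjusted single-outcome test rejects with probability P(|1.9r + √(1 − r²)·e| > 1.96), with e standard normal: 7.7% at r = 0.3 and 12.2% at r = 0.5. That conditions on an imbalance chosen just below the threshold. Averaged over randomisations the rate is 3.9% to 4.9%, so the documents do not support a claim of inflation.

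**On reading.** The protocol does not say that only imbalanced factors are adjusted, and does not tie imbalance to p<0.05. Both are inferred, from the absence of any other efficacy covariate rule and from the blanket 0.05 level. If imbalance is to be judged some other way, the criterion is undefined and the set still depends on the data. No measure of psychiatric diagnosis severity is specified, so forced categorisation is also an inference.

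**On context.** This is a pilot without a power calculation, and no confirmatory decision rests on it. That lowers the stakes. But Section D hypothesises significant superiority on the efficacy outcomes, and the rule governs those analyses.

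**Conclusion.** The point holds as a fault in a stated rule, not as a detail left for a statistical analysis plan. Choosing efficacy covariates from observed baseline imbalance makes the model depend on the data, and the test does not measure prognostic value. On the p<0.05 reading, each named factor is omitted in about 95% of trials, and imbalances up to about 0.39 SD or 19 percentage points go unadjusted.

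Overall type I error is not inflated. The precision loss is modest, about 1% to 5% in standard error under the assumed correlations. It depends on how far the factors predict post-baseline outcome beyond its own baseline, which the protocol does not tell us. The change is worth making because it is nearly free and the plan already adjusts its safety models for two of the three factors without condition.

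**What to change.** In both places in G.3, replace the imbalance rule with a prespecified one:

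- Adjust the efficacy models for education, psychiatric diagnosis severity and substance use whatever the baseline comparison shows, keeping factors continuous where they are measured so.
- Let the covariates act on post-baseline values, either through covariate-by-time terms or through a model of the week 8 and 3-month outcomes adjusted for the baseline outcome and the covariates. Main effects alone would leave the continuous change contrast essentially as it is.
- Omit a factor where it is itself the outcome being modelled, since its baseline is already in the model. This concerns psychiatric severity and substance use, which F.5 lists as secondary outcomes.
- Present baseline characteristics descriptively by arm, without tests of randomisation.
- Report the unadjusted model as a sensitivity analysis.

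Cost: a few sentences and no new data. The adjustment uses a few degrees of freedom; the exact number depends on the education categories and time terms. G.3 anticipates attrition ("We conservatively anticipate that 15% of participants will dropout during the 8 week RCT", then another 5% at 3 months), leaving about 96 × 0.80 = 77 women at the last visit, so the covariate list should stay short. In the logit models the adjusted odds ratio is conditional on the covariates and differs in meaning from the unadjusted one, which the report should say.
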